10.3 Biomarkers

Serum/plasma will be collected for assessment of biomarkers at Visits 2, 4, 5 and 7.

Biomarkers to be assessed are:

Potential mechanistic / pharmacodynamic markers	• Monocyte chemo-attractant protein–1 (MCP-1)
	 Interleukin (IL)-1β
	• IL-6
	• IL-17A

Protocol No.: ORV-PF-01 Final V4.0 (US) Page 50 of 85

DRVEPITANT	NeRRe Therapeutics Ltd
Potential markers of	

Protocol No.: ORV-PF-01

Potential markers of disease progression	• C3M	
--	-------	--

10.4 **Pharmacokinetic Assessments**

A single 'spot' blood sample for analysis of plasma or vepitant concentrations will be collected at Visits 4, 5 and 7.

Details of PK blood sample collection (including volume to be collected), processing, storage and shipping procedures will be provided in the Laboratory Manual.

10.5 Adverse events

10.5.1 Definitions

Adverse Event (AE)

Any untoward medical occurrence in a subject or clinical trial subject administered an IMP and which does not necessarily have a causal relationship with this treatment. An AE can therefore be any unfavourable and unintended sign (including an abnormal laboratory finding, for example), symptom, or disease temporally associated with the use of an IMP, whether or not considered related to the IMP.

Adverse Drug Reaction

All AEs considered to be untoward and unintended responses to an IMP related to any dose should be considered adverse drug reactions. The definition also covers medication errors and uses outside what is foreseen in the protocol, including misuse and abuse of the product. The phrase "responses to an IMP" means that a causal relationship between the IMP and an AE is at least a reasonable possibility, i.e., the relationship cannot be ruled out.

Serious Adverse Event (SAE)

An adverse event that:

- Results in death
- Is life-threatening (i.e., the subject was at risk of death at the time of the event; it does not refer to an event which hypothetically might have caused death if it was more severe)
- Requires in-patient hospitalisation or prolongation of existing hospitalisation (see explanation below)
- Results in persistent or significant disability/incapacity
- Is a congenital anomaly/birth defect
- Is considered to be an important medical event

Based upon medical and scientific judgment, important medical events that may not be immediately life-threatening, or result in death or hospitalisation, but may jeopardize the subject and/or¹² may require intervention to prevent one of the other outcomes listed in the definition above may be considered a SAE.

16-MAY-2024

Protocol No.: ORV-PF-01

¹² The definition varies between regulatory jurisdictions

Hospitalisations are defined as initial or prolonged admissions that include an overnight stay. Hospitalisation or prolonged hospitalisation for technical, practical, or social reasons, in the absence of an adverse event is not an SAE and neither is attendance at an Emergency Room / Accident and Emergency Department that takes place in the evening or night and does not result in formal admission to the hospital.

Adverse Events of Special Interest

For the purposes of this study, any "respiratory decline" event that doesn't meet the definition of an SAE is to be considered an adverse event of special interest (AESI) and should be reported by the investigator to the Sponsor in an expedited manner by completing the AESI form and sending it by email to the medical monitor. This will enable the Sponsor to monitor for potentially relevant safety findings that do not meet the definition of serious. Non-serious respiratory decline events include (but are not limited to) the following:

- Unscheduled visits to a healthcare professional for respiratory status deterioration.
- Urgent care visit for respiratory status deterioration.

In addition, any adverse event relating to suicidal ideation or suicidal behaviour that doesn't meet the definition of an SAE is to be considered an AESI and should be reported by the investigator to the Sponsor in an expedited manner by completing the AESI form and sending it by email to the medical monitor.

Unexpected Adverse Drug Reaction

An adverse reaction, the nature or severity of which is not consistent with the reference safety information section of the current version of the Investigator's Protocol.

Reports which add significant information on the specificity, increase of occurrence, or severity of a known, already documented serious adverse reaction may also constitute unexpected events.

Suspected Unexpected Serious Adverse Reaction (SUSAR)

A serious adverse event that is suspected to be related to the administered medicinal product and the nature or severity of which is unexpected.

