### 8 SAFETY ANALYSES

Safety data will be summarised descriptively for each treatment. That is, safety data will be summarised for two doses of orvepitant (10 mg and 30 mg separately), and two placebo groups separately by cohort.

No formal inferential tests will be performed on safety data.

Safety analysis will be carried out using the SS population.

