### 8.1 ADVERSE EVENTS

Adverse events will be coded using the latest available version of MedDRA (v26.0 or higher). All treatment-emergent AEs (TEAEs) from the start of study drug dosing will be collected. A TEAE is any AE that first occurred or worsened in severity following first dose. AEs that start during the wash-out period will be assigned to the treatment received during Treatment Period A for TEAE reporting; AEs that start following first dose in Treatment Period B up to end of follow-up will be assigned to the treatment received during Treatment Period B for TEAE reporting.

The following AE summaries will be presented:

- An overall summary table, including the number of events and number and percentage of subjects with:
  - o TEAEs
  - Subjects with at least one TEAE
  - Study drug-related TEAEs

Page 34 of 50

- Serious TEAEs
- o TEAEs with an outcome of death
- o Treatment-emergent AESIs
- Severe TEAEs
- o TEAEs leading to study drug discontinuation
- TEAEs by SOC and PT. This table will have a section for overall, and two subgroup sections for concomitant use of disease modifying therapies (yes, no [nintedanib or pirfenidone])
- Serious TEAEs by SOC and PT
- Treatment-emergent AESIs by SOC and PT
- TEAEs leading to study drug discontinuation by SOC and PT
- Related TEAEs by SOC and PT
- Maximum severity of TEAEs by SOC and PT

Non-treatment emergent AEs and TEAEs will be listed.

In addition, the following subject listings will be provided as tables:

- Deaths
- Serious TEAEs
- AESIs
- TEAEs leading to study drug discontinuation

For all AE tables summarised by SOC and PT, a subject contributes only once to the count for a given AE on the SOC level and on the PT level within SOC. SOC and PT levels will be sorted in descending order of frequency (subject count), followed by descending order of frequency (event count), followed by alphabetical order.

AEs will be classified as either related or unrelated to study medication. AEs with missing relationship to study drug are counted as related in the summary tables.

In the summary by severity, subjects reporting AEs at different severities will be counted only once at the highest severity reported within an AE level (SOC or PT). Severity categories will comprise of mild, moderate and severe.

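### The AESI summaries count only non-serious respiratory decline and suicidality, and no planned output totals respiratory decline by treatment whatever its seriousness

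*Protocol*

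**What the plan says.** Protocol 10.5.1 creates two kinds of adverse event of special interest (AESI). For the first, any respiratory decline "event that doesn't meet the definition of an SAE is to be considered an adverse event of special interest (AESI". For the second, "any adverse event relating to suicidal ideation or suicidal behaviour that doesn't meet the definition of an SAE is to be considered an AESI". It gives a reason after the respiratory rule: "This will enable the Sponsor to monitor for potentially relevant safety findings that do not meet the definition of serious". The examples of non-serious decline are unplanned or urgent-care attendances because breathing has worsened, and the list is expressly open. There is no list of preferred terms.

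The SAE definition in the same section includes death and an event that "Requires in-patient hospitalisation or prolongation of existing hospitalisation".

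SAP 8.1 uses AESIs in three outputs: a row in the overall summary, a table titled "Treatment-emergent AESIs by SOC and PT", and a subject listing. It also plans "Serious TEAEs by SOC and PT" and, for all events together, "TEAEs by SOC and PT. This table will have a section for overall", plus a table of maximum severity and listings of deaths and serious TEAEs. SAP 8 sets the columns: "safety data will be summarised for two doses of orvepitant (10 mg and 30 mg separately), and two placebo groups separately by cohort".

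**The concern.** A reporting trigger and a safety summary have different jobs. The trigger needs only the events that the SAE route would miss, so leaving out serious events is sensible. A by-treatment summary of respiratory decline should cover the whole range of the event, and its serious end matters most.

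When the trigger category becomes the summary, a worse outcome moves a subject out of the count. If one treatment turned non-serious declines into admissions, its AESI count would fall.

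Safety is one of the two primary objectives (Protocol 6.1), and respiratory decline is one of only two event types that the sponsor singled out. Serious respiratory events are foreseeable: Protocol 5.2 describes a progressive disease with a median life expectancy of 2 to 5 years after diagnosis, and Protocol 11.4 lists death among the expected intercurrent events. With 37 evaluable subjects per cohort, a few events can change the direction of a comparison.

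**Working it through.** **Step 1. Which definition governs the SAP tables?** The SAP does not define AESI, and the term is not in its abbreviation list. Protocol 11.6 gives the SAP precedence where the two texts differ, but the SAP offers no competing text. The protocol's non-serious definition therefore applies.

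**Step 2. Where does each event appear?**

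| Event | AESI outputs | Serious TEAE outputs | All-TEAE and severity tables | Identified as AESI-type? |
|---|---|---|---|---|
| Respiratory decline, non-serious | Yes | No | Yes | Yes, through AESI status |
| Respiratory decline with admission | No | Yes | Yes | No |
| Respiratory decline, fatal | No | Yes, and death row and listing | Yes | No |
| Suicidality, non-serious | Yes | No | Yes | Yes, through AESI status |
| Suicidality, serious | No | Yes | Yes | No |

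The safety endpoints (Protocol 8.3, SAP 3.4) and Protocol 11.9 add no summary of respiratory decline.

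**Step 3. Can the total be recovered?** At event level, AESI and SAE do not overlap:

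all respiratory decline events = non-serious (AESI) events + serious events.

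The AESI outputs give the first term. No output identifies the second as a group. At subject level, let a be the subjects with a non-serious decline and s those with a serious one. One subject may have both, so

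max(a, s) ≤ subjects with any decline ≤ a + s.

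Even these limits need s, which is not tabulated.

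**Step 4. Illustration.** The documents give no event counts, so these are assumptions. In a cohort of 37, suppose that 5 subjects on each treatment have one respiratory decline event each, with no suicidality events.

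- Placebo, 1 serious: AESI count 5 − 1 = 4.
- Orvepitant, 3 serious: AESI count 5 − 3 = 2.

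The AESI row reads 2 versus 4, although the totals are 5 versus 5 and the serious events are 3 versus 1 against orvepitant. With placebo held at 1 serious and k serious on orvepitant, the AESI count on orvepitant is 5 − k:

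| k | 0 | 1 | 2 | 3 | 4 | 5 |
|---|---|---|---|---|---|---|
| Orvepitant AESI count | 5 | 4 | 3 | 2 | 1 | 0 |
| Placebo AESI count | 4 | 4 | 4 | 4 | 4 | 4 |
| Any decline, each treatment | 5 | 5 | 5 | 5 | 5 | 5 |

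For every k above 1 the AESI row favours the treatment with more serious events.

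Now suppose that a reader knew s but not the overlap. The limits for the k = 3 counts would be max(2, 3) = 3 to 2 + 3 = 5 on orvepitant, and max(4, 1) = 4 to 4 + 1 = 5 on placebo. That does not settle which treatment had more subjects with a decline.

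**The case against.** The case on the other side has real force.

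- A reader might infer that serious respiratory declines drop out of the safety report, or appear only in one general SAE table. The documents do not support that. They also enter the all-TEAE table, the maximum-severity table, the overall serious, severe and fatal rows as applicable, and the listings.
- In the illustration, the 3 versus 1 serious events would enter the serious-TEAE row of the same overall table that shows the AESI row. A careful reader has a warning in view.
- SAP 8.1 counts a subject once per SOC and once per PT within SOC. The all-TEAE table therefore already gives de-duplicated counts across seriousness for each coded term.
- AESIs are not a listed safety endpoint, no inferential safety test is planned, and a DSMB oversees safety.
- The non-serious limit is deliberate and explained, so a reader who took the protocol definition itself to be a mistake would go too far.

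All of this stands, and it limits the point to a missing grouping. It does not remove the point. Protocol 10.5.1 describes respiratory decline by clinical deterioration and not by coding, so no SOC or PT row equals it. A SOC row may include other respiratory complaints and miss declines coded elsewhere. A reader could try to rebuild the group from the listings, but after unblinding that choice would be made with the treatments known.

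There is also a version limit. SAP V1.0 (14 March 2024) was written against protocol V3.0/3.1, and the protocol at hand is V4.0 (16 May 2024). The AESI wording that the SAP relied on cannot be checked. SAP 1 foresees revision after amendments, and read together the two present documents leave the gap.

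**Conclusion.** The point holds as a gap in presentation that is cheap to close. Followed as written, the AESI outputs measure non-serious respiratory decline and suicidality only. Their count falls as declines become serious, and no planned output gives subjects with any respiratory decline by treatment.

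The number of events affected equals the number of serious respiratory declines and serious suicidality events, which the documents do not state and which may be small over two 28-day periods. The illustrative counts show direction only.

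The conclusion rests on the protocol V4.0 definition governing the SAP, and on SAP 8.1 being the full list of adverse event outputs. Detailed table specifications are left to later documents (SAP 13.1). Neither the efficacy analysis nor any hypothesis test is affected.

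**What to change.** Keep the definition in Protocol 10.5.1 as the expedited-reporting trigger. In SAP 8.1:

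1. Add to the overall summary and to the AESI tables two separate lines: *respiratory decline, serious or non-serious* and *suicidal ideation or behaviour, serious or non-serious*. Give subjects and events by treatment, with a serious/non-serious split.
2. Identify the serious events that belong in each line with a flag or term list agreed before unblinding at the planned blinded data review meeting. SAP 4.3 already requires certain respiratory adverse events to be identified for the Per Protocol Set, and SAP 13.2 includes the medical monitor in the review of the outputs for that meeting.
3. Label the existing AESI row, table and listing as non-serious AESIs.

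The cost is SAP wording, one flag or list, and a few table rows, with no new data. The downside is a small amount of clinical judgement in flagging SAEs, because respiratory decline has no term list. Making that judgement blinded and recording it at the meeting keeps it independent of treatment.

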10.5.2 Assessment of Severity

The severity (intensity) of each adverse event will be classified as:

Mild Awareness of sign or symptom, but easily tolerated by the subject

Moderate Sign or symptom causes discomfort, but does not interfere with the subject's

normal activities

Severe Sign or symptom of sufficient intensity to interfere with subject's normal

activities

10.5.3 Assessment of Causality

A determination will be made of the relationship (if any) between an AE and the study drug. A causal relationship is present if a determination is made that there is a reasonable possibility that the AE may have been caused by the drug. AEs will be classified as either related or unrelated.

10.5.4 Adverse Event Reporting

Adverse events may be volunteered spontaneously by the subject, or discovered as a result of general, non-leading questioning. Adverse events occurring from the Screening Visit up to the final

Protocol No.: ORV-PF-01 Final V4.0 (US) Page 52 of 85

study visit will be recorded. All AEs should be recorded in the eCRF and in the subjects' source notes.

Any SAE occurring from the time the Screening Visit until 30 days after the last dose of IMP must be reported immediately (within 24 hours of the investigator becoming aware of it) and recorded on the SAE Form. Detailed instructions for the reporting of SAEs will be provided. All subjects with an SAE must be followed up and the outcomes reported. The investigator must supply the Sponsor and the relevant regulatory and ethics authorities with any additional requested information (e.g., autopsy reports and terminal medical reports). Any follow-up information on a previously reported SAE will also be reported within 24 hours of awareness.

If the Investigator does not have all information regarding an SAE, he/ she will not wait to receive additional information before reporting the event and completing the appropriate data collection form. The Investigator will always provide a preliminary assessment of causality at the time of the initial report as described in Section 10.5.3.

The primary mechanism for reporting SAEs will be a paper collection form.

'Scan & email' of the SAE form is the preferred method to transmit this information to the project contact for SAE receipt although fax transmission is also acceptable. In rare circumstances and in the absence of email capability or fax equipment, notification by telephone is acceptable, with a copy of the SAE data collection form sent by overnight mail. Initial notification via the telephone does not replace the need for the Investigator to complete and sign the SAE data collection form within the designated reporting periods.

NeRRe is required to expedite to regulatory authorities reports of SUSARs in line with the relevant legislation. Fatal or life-threatening SUSARs must be reported within 7 calendar days and other SUSARs within 15 calendar days.

All investigators will receive a safety letter notifying them of relevant SUSAR reports. If required by local reporting regulations, each Investigator must then notify his or her relevant Institutional Review Board (IRB) or Research Ethics Committee (REC). NeRRe will submit to the regulatory authorities all safety updates and periodic reports, as required by applicable regulatory requirements.

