Hull Airway Reflux Questionnaire (HARQ) completed at Baseline and in Week 4 of each treatment period	Secondary efficacy endpoints • Mean change from Baseline to Week 4 in the HARQ score
SAFETY	ASSESSMENTS AND ENDPOINTS
SAFETY ASSESSMENTS	SAFETY ENDPOINTS
Pulmonary function tests measured in the clinic at: • Screening, Baseline, End of Wash-out, Week 4 of each treatment period and Follow-up. Adverse events recorded throughout the study (from Screening Visit to the Follow-Up Visit)	 Change from Baseline in forced vital capacity (FVC), forced expired volume in one second (FEV1), peak expiratory flow rate and vital capacity (VC) Number of treatment emergent adverse events Number of treatment emergent serious adverse events Number of treatment emergent adverse events resulting in treatment discontinuation
	Severity of treatment emergent adverse events Number of treatment emergent related adverse events
Physical Examination recorded: • At Screening, Baseline and Follow-up.	Treatment emergent changes in physical examination will be recorded as adverse events
Vital Signs (pulse rate, systolic and diastolic blood pressure, temperature, arterial oxygen saturation) recorded: • At Screening, Baseline, End of Wash-out, Week 4 of each treatment period and Follow-up. Additionally, weight recorded: • At Baseline and Follow-up.	Mean change from Baseline in each vital sign: Systolic blood pressure Diastolic blood pressure Pulse rate Temperature Arterial oxygen saturation Weight Note: Clinically significant changes in vital signs are recorded as adverse events

Protocol No.: ORV-PF-01

Product: CONFIDENTIAL Protocol No.: ORV-PF-01 ORVEPITANT NeRre Therapeutics Ltd

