 - b. Strong or moderate inducers of CYP3A4 are not allowed from Screening until 1 week after the last dose of study medication
 - c. Strong or moderate P-glycoprotein inhibitors are not allowed from Screening until 1 week after the last dose of study medication
 - d. Angiotensin converting enzyme (ACE) inhibitors are not allowed within 3 months of Screening and throughout the study.
 - e. Other treatments for cough management (opioids, dextromethorphan, gabapentin, pregabalin, baclofen, antihistamines, thalidomide, benzonatate or tricyclic antidepressants (e.g. amitriptyline)) are not allowed from 4 weeks before the Baseline visit until Visit 8. Medications in these classes may be continued provided they have been prescribed solely for the management of another comorbidity and the dose has been stable for at least 4 weeks before the screening visit.
 - f. The use of other NK₁ antagonists (e.g., aprepitant, fosaprepitant, rolapitant) is not permitted for any reason from 4 weeks before the Baseline visit until completion of Visit 8
 - g. Immune-suppressant drugs and systemic corticosteroids taken for co-morbidities are permitted provided the dose has been stable for at least 2 weeks before the screening visit and they are expected to be used at this dose throughout the study. Any other use is prohibited.
 - h. Supplemental oxygen is permitted provided it has been used for at least 2 weeks before the screening visit and is expected to be used throughout the study.

Final V4.0 (US) Protocol No.: ORV-PF-01

⁸ The investigator should judge the clinical relevance of any abnormal laboratory parameters in the context of the subject's current and past medical history, and any know contributing factors

- 13. Participation in any clinical research study evaluating another investigational drug or therapy within 30 days or within 5 half-lives (whichever is longer) of the investigational drug prior to Screening. If the subject was in an observational clinical study, no washout is required
- 14. Subjects who have previously received orvepitant at any time
- 15. Known allergy to any of the excipients used in the investigational medicinal product (IMP) (orvepitant or placebo tablets)
- 16. Subjects who, in the opinion of the Investigator, should not participate in the study for any other reason.
- 17. Subjects who are dependent on the Sponsor, CRO or investigator for employment of education.

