8.7 Study Visits

8.7.1 Screening

Subjects will provide informed consent before any screening procedures are undertaken. If the subject is taking a prohibited concomitant mediation which can be safely discontinued, then

Protocol No.: ORV-PF-01 Final V4.0 (US)

CONFIDENTIAL Protocol No.: ORV-PF-01
NeRRe Therapeutics Ltd

informed consent must be taken first. The formal screening visit may then be delayed to allow completion of the concomitant medication wash-out period such that the screening assessments are completed within 28 days before the Baseline visit.

The screening period will last a minimum of 14 days so that the baseline electronic diary (eDiary) assessment can be completed.

The Screening visit will include the following assessments to determine the subject's eligibility for inclusion into the study:

- Full physical examination, 12 lead ECG, vital signs, pulse oximetry and spirometry (FEV₁ and FVC)
- If the subject has not had diffusion capacity of carbon monoxide (DLCO) measured within 12 months before screening, then this should be undertaken at the screening visit⁹.
- Recording of the subject's medical history, and prior and concomitant medication use, in particular other concomitant respiratory medications, both prescribed and/or over the counter medications
- Blood sampling for clinical chemistry and haematology, and urine sample collection urinalysis

Subjects should be carefully pre-screened so that the outcome of most eligibility criteria can be anticipated at the formal screening visit. If necessary, non-routine assessments (e.g., DLCO) should be pre-arranged for the screening visit.

Subjects who satisfy all criteria (other than safety laboratory tests the results of which are unlikely to be immediately available) and in whom no clinically relevant laboratory abnormalities are anticipated can be provided with the eDiary and be trained on its use (including review of a patient information video). The eDiary should be completed for 14 days before the subject returns for the baseline visit.

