9.4.2 Dose interruption

If a subject experiences an AE which the investigator believes is treatment related and which the subject finds intolerable, a break in dosing of up to 1 week is permitted. If on reintroduction of the IMP, the AE recurs and remains intolerable the IMP will then be withdrawn altogether. A break in dosing will not result in extension of the overall dosing period.

9.5 **Duration of Subject Participation**

The total planned duration of participation in the study for an individual subject is up to 17 weeks, which comprises the following:

- Initial Screening phase of up to four weeks (excluding any additional periods for washout of prohibited concomitant medications)
- 4 weeks each for Treatment Periods A and B
- 3 weeks for the wash-out period
- 2 weeks for follow up

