9.10.2 Contraception

Female subjects of childbearing potential are excluded from the study and hence there are no contraceptive requirements for them.

Male subjects who are sexually active with a female partner of child-bearing potential (i.e., the partner is not surgically sterilised or postmenopausal) must agree to use a condom for the duration of participation in the study and for 30 days after the last dose of study medication.

Protocol No.: ORV-PF-01 Final V4.0 (US) Page 42 of 85

CONFIDENTIAL ORVEPITANT

Product:

Protocol No.: ORV-PF-01 NeRRe Therapeutics Ltd

STUDY SCHEDULE 10.

Table 2: Schedule of Events

	Screening	Baseline	Treatment Period A	t Period A	End of Wash-	Treatmen	Treatment Period B	Follow-up/
	A ISIL		Week 2f	Week 4	Period B	Week 2 ^f	Week 4	Termination ^b
Visit (V) Number	1	2	3	4	5	9	7	œ
Timing of visit	Within 14 to 28 days of V2	Day 0	14 days after V2	28 days after V2	21 days after V4	14 days after V5	28 days after V5	14 days after V7
Allowable window	N/A	0	±3 days					
Informed Consent ^a	X							
Medical History & demographics	X							
Physical examination	X	X°						Χc
Pulmonary function tests (spirometry)	χi	X		X	X		X	X
Inclusion/exclusion criteria	X	$^{ m pX}$						
Concomitant medication review	X							XX
Vital signs ^e	X	X		X	X		X	X
12-lead ECG	X	X		X	X		X	X
AE recording		X						XX
Issue eDiary/Training/Compliance check	X	X	X	X	X	X		
Randomisation		X						
eDiary completion (once daily) ⁱ	X						X	
Study drug dispensing/training		X			X			
Study drug collection/compliance check				X			X	
Ambulatory cough monitoring		X		X			X	
Daily dosing (evening before bed)			X _h	X		X	X	
Leicester Cough Questionnaire		X		X	X		X	
Hull Airway Reflux Questionnaire		X		X			X	
K-BILD Questionnaire		X		X	X		X	
PROMIS SF SD 8b		X		X	X		X	
Hospital Anxiety and Depression Scale		X		X	X		X	
Global ratings of status/change in cough		Xg	X	X	X	X	X	X
Biomarker samples		X		X	X		X	
Clinical chemistry and haematology	X	X		X	X		X	X
Blood sample for orvepitant concentration				X	X		X	
Urinalysis	X	×		×	×		×	X

Page 43 of 85 Final V4.0 (US) Protocol No.: ORV-PF-01 16-MAY-2024

CONFIDENTIAL

Product: ORVEPITANT

Protocol No.: ORV-PF-01 NeRRe Therapeutics Ltd

rs	Informed consent will be obtained prior to any screening procedures being performed. Consent can be obtained prior to the Screening Visit or at the actual visit.

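### AE recording and SAE reporting start at the Screening Visit, but some consented patients stop a prohibited drug for the study before it, leaving a reporting gap of up to about 3 months

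*Protocol*

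**What the plan says.** **When collection starts.** Protocol 10.5.4 (Adverse Event Reporting) records "Adverse events occurring from the Screening Visit up to the final" study visit. For serious events it says: "Any SAE occurring from the time the Screening Visit until 30 days after the last dose of IMP must be reported immediately", and defines immediately as within 24 hours of the investigator becoming aware. The synopsis agrees on the start for AEs: "Adverse events recorded throughout the study (from Screening Visit to the Follow-Up Visit".

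**When the study first affects the patient.** Protocol 8.7.1 (Screening) provides for drugs that the protocol does not allow. "If the subject is taking a prohibited concomitant mediation which can be safely discontinued, then" consent has to come first. After that, "The formal screening visit may then be delayed to allow completion of the concomitant medication wash-out period", timed so that the screening assessments fall in the 28 days before Baseline. Footnote a to the Schedule of Events (Table 2) confirms the order: "Consent can be obtained prior to the Screening Visit or at the actual visit". Section 9.5 (Duration of Subject Participation) leaves this time out of the planned total by describing the first component as "Initial Screening phase of up to four weeks (excluding any additional periods for washout of prohibited concomitant medications".

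**How long the drugs must be off.** The longest stated lead time is in exclusion criterion 12d: "Angiotensin converting enzyme (ACE) inhibitors are not allowed within 3 months of Screening and throughout the study". Drugs used for cough, and other NK1 antagonists, must be off from 4 weeks before Baseline (12e, 12f). CYP3A4 inducers and P-glycoprotein inhibitors are barred from Screening, with no lead time given (12b, 12c). CYP3A4 inhibitors are barred only from Visit 2 (12a).

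**The concern.** These two sets of rules do not meet. On the route in 8.7.1 the sequence is consent, stop the drug, wait, Screening Visit. For such a patient, stopping the drug is the first thing the study brings about, and it happens before either reporting window opens. No section of the protocol or SAP asks for AEs or SAEs to be collected between consent and Screening, and the Schedule of Events has no contact in that interval.

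What is at stake is oversight of participant safety. A hospitalisation or death after a drug was stopped in order to enter this trial would fall outside the SAE rule in 10.5.4. It would carry no 24-hour reporting duty and no follow-up duty. The DSMB may recommend changes to study conduct (10.7), but the protocol gives no route by which such events would reach it.

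**Working it through.** **The plan's own figure.** Section 9.5 gives a planned participation of up to 17 weeks. Its components add up: 4 (screening) + 4 + 4 (treatment periods) + 3 (wash-out between periods) + 2 (follow-up) = 17 weeks, or 17 × 7 = 119 days. The sum works only with the pre-screening drug wash-out left out, as 9.5 states.

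**Uncovered interval.** This is the drug-free time that must elapse before the Screening Visit, taking the drug to be stopped once consent is given and Screening to follow as soon as the rule permits.

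- *ACE inhibitor:* 3 months before Screening. 3 × 52/12 = 13 weeks, about 90 days. With the 17 planned weeks, consent to follow-up would span about 13 + 17 = 30 weeks, of which the first 13 have no AE or SAE collection.
- *Cough-active drugs and other NK1 antagonists:* 4 weeks (28 days) before Baseline, less a screening period of 14 to 28 days (8.6). 28 − 28 = 0 days at one end and 28 − 14 = 14 days at the other.
- *CYP3A4 inducers and P-glycoprotein inhibitors:* barred from Screening with no lead time, so the gap is whatever time the site allows. It cannot be computed from the documents.
- *CYP3A4 inhibitors:* barred only from Visit 2, so a stop can fall wholly inside the existing window. The required gap is 0.
- *No prohibited drug to stop, and consent at the Screening Visit:* 0.

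**What else would capture an event in the gap.**

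- Section 7.4 requires a reason for withdrawal for anyone who has consented, and an adverse event is one of the listed reasons. A patient can thus be recorded as withdrawn for an AE that 10.5.4 does not ask anyone to record.
- Section 8.7.2 collects a limited data set on patients who leave after consent and before randomisation.
- Section 10.2.1 takes medical history at Screening and all medication from the previous six months, which covers the 3-month ACE-inhibitor interval.
- Section 10.2.2 sends abnormalities found on the Screening physical examination to the medical history page, not the AE page.

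None of the four starts 24-hour reporting or SAE follow-up, and the last two need the patient to reach Screening.

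**The case against.** The strongest reply is that the gap is narrow and already partly covered. Section 8.7.1 is conditional: it applies only where a drug can be safely discontinued, and the Screening Visit may, not must, be delayed. Three months is the figure for one drug class, and for cough drugs the gap can be zero. Section 10.5.1 defines an AE in a subject given the IMP, so starting at Screening already goes further than that definition requires. Detailed SAE instructions and the DSMB Charter are separate documents and may deal with this. Most of this stands, and it limits the size of the point. It does not close the gap, because the explicit text of 10.5.4 sets the start, and the protocol, by collecting from Screening, already accepts that events before the first dose matter.

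A reader might also infer more than the documents support:

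- *That these harms would go entirely unseen.* Sections 7.4, 8.7.2, 10.2.1 and 10.2.2 give partial capture.
- *That the AE row of Table 2 and of SAP Table 1 starts at Baseline, leaving the 14 to 28 days of screening uncovered for everyone.* The row cannot be read reliably in the extracted text. The synopsis, 10.2.2 and 10.5.4 all set the start at Screening, and a first mark at Baseline would fit with Baseline being the first later visit at which AEs are reviewed.
- *That treatment-emergent AE classification suffers because starting severity is unknown.* The Screening history supplies it, as for any pre-existing condition.

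**Conclusion.** The point holds as a participant-safety reporting gap limited to patients who consent and then stop a prohibited drug before a delayed Screening Visit. For them there is no AE recording and no 24-hour SAE reporting between consent and Screening. The interval is up to about 3 months for an ACE inhibitor, 0 to 14 days for cough-active drugs, and undetermined for other classes barred from Screening.

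The figures assume that the drug is stopped because of the study, after consent, and that Screening follows as soon as the rule allows. The documents do not say how many patients take this route, so no total exposure can be given. The conclusion also assumes that the separate SAE instructions and the DSMB Charter do not already start collection at consent.

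The gap should not be read as a threat to the efficacy or safety comparison. It precedes randomisation, and the safety tables in SAP 8.1 are built on events that begin or worsen after the first dose.

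**What to change.** Amend 10.5.4 and the synopsis so that SAEs, and AEs attributed to study-required withdrawal of medication, are recorded and reported from informed consent. All other AEs would start at the Screening Visit, as now. Name study-required withdrawal explicitly as a possible cause, because 10.5.3 assesses causality only against the study drug and would leave such an event simply unrelated. Check the AE row of Table 2 and of SAP Table 1 against the amended text, and bring the SAE instructions into line.

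The cost is amendment wording and a few extra AE or SAE records. No visit, procedure or rule on medication changes. SAP 8.1 already provides for listing non-treatment-emergent AEs, and its treatment-emergent tables would be unaffected. Two limits remain. With no added contact, non-serious events will still mostly be recalled at Screening, so the main gain is in serious events. The change also helps only patients who consent after it takes effect: the SAP of March 2024 notes that data from 25 subjects had already been used for the sample size re-estimation.
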